Official Title: Examining the Impact of Stress on the Emotionally Reinforcing Properties of Alcohol in Heavy Social Drinkers: A Multimodal Investigation Integrating Laboratory and Ambulatory Methods

NCT number: NCT03449095

Document Date: 4/24/2024

Study Protocol

Participants in this study will be male and female social drinkers, age 21-30. To be eligible, all participants will need to identify at least one eligible same-gender friend. Participants will be excluded from participation if they have a history of adverse reaction to the amount of beverage employed in the study, if they have a history of alcohol treatment or of major problems associated with alcohol, or if they are especially light drinkers or abstainers. Participants must also report comfort with the dose of alcohol administered in the study. Individuals will be excluded if they have medical conditions that contraindicate alcohol administration, if they are illiterate, or if they are non-fluent English speakers. Participants must not be dependent on any substance other than nicotine or caffeine, and must not qualify for severe Alcohol Use Disorder, as assessed at the time of study screening via DSM-V. Females who are pregnant or trying to conceive will be excluded.

The laboratory portion of this study involves an examination of dyadic interaction. Participants will be paid a maximum of \$100 for completing the laboratory portion of the study. Once at least two members of a friendship group qualify for participation during screening, they are invited back for an experimental laboratory session. Study advertisements allow for friend groups larger than 2 in order to account for ineligible subjects and/or dropout. Two friend dyads are invited to the laboratory for simultaneous beverage administration sessions. On the day of the session, they are randomly assigned to consume alcohol in the company of their own friend, or of the friend of the other participant (an individual with whom they are unacquainted). We adopt this procedure—in which all participants are recruited through a single mechanism—to ensure that the populations of individuals in friend and stranger conditions are comparable and unaffected by selection bias. Within the stranger condition, we will adopt procedures we have used previously to ensure these participants are unacquainted (i.e., all participants are introduced prior to beverage administration and backup participants are invited to all stranger sessions in case the primary 2 participants are previously acquainted).

Dyads will be randomly assigned to receive either a moderate dose of alcohol or a control beverage. The dose will be adjusted for participants' weight and gender and is designed to produce a peak BAC of .08% (0.82-g/kg males; 0.74-g/kg females). Alcoholic beverages will be administered as a soda/juice-vodka cocktail, and control participants will consume an isolvolumic amount of soda/juice. In order to model drinking conditions as they most often manifest outside the laboratory (Senchak et al., 1998), both members of the dyad are assigned to the same beverage condition. We chose not to deceive participants in the control condition about the content of their beverages.

Participants consume their beverages in 3 equal parts over 36 minutes. Experimenters enter the room to refill drinks at 12 and 24 minutes. During the dyadic drink period, video cameras are trained on each participant. Participants are initially told that cameras are monitoring their drink consumption, and only later provide consent for their behaviors to be analyzed from video using FACS. Immediately after the drink administration period, participants are brought into separate rooms to complete self-reports, including positive and negative mood, and perceived social reinforcement. Participants in the control condition are allowed to leave after completing the rest of the laboratory procedures. Participants in the alcohol condition stay until their BAC drops to 0.00 and are breathalyzed at 15-min intervals.

Participants may also be offered the opportunity to participate in an additional ambulatory study. This opportunity may be offered to a subset of individuals who complete the laboratory study, as well as individuals recruited from the local community. Participants will sign a separate consent form outlining procedures involved in ambulatory assessment.

The ambulatory assessment techniques used in this study were selected for their capability to reliably and unobtrusively measure key constructs of interest. Data from the SCRAM transdermal alcohol monitor will be used to assess alcohol use during the ambulatory assessment period, lasting 14 days. Data from transdermal alcohol monitors will be converted into estimations of BAC using machine learning algorithms developed by our laboratory (Fairbairn et al., 2020). During the ambulatory assessment period, participants will complete self-reports of their mood and take photographs of themselves and their surroundings on their smartphones or, in the event they do not own a smartphone, on one of our lab's iPod touch devices. Participants will complete self-report surveys regarding their mood, their social surroundings, and their alcohol consumption in response to random "pings" or alarms sounding 8 times during their waking hours. Participants will be asked to attend 2 additional (brief) laboratory visits during the ambulatory assessment period—a total of 3 visits, including the original lab orientation session. The first of these visits will take place approximately halfway through the ambulatory assessment period. During this visit, the fit of the transdermal sensors will be assessed, and they will receive feedback on their compliance with ambulatory assessment procedures. At the end of the ambulatory assessment period, participants will review the photographs they took during ambulatory assessment and report their level of acquaintance and relationship quality with each individual depicted therein. During their final visit, they will return the transdermal equipment. Participants will be paid up to \$200 for completion of the ambulatory assessment period.

Statistical Analysis Plan

Analyses will be conducted using Hierarchical Linear Modeling (HLM; Raudenbush & Bryk, 2002). Models for facial data will involve 3-levels—within-person, between-person, and dyad-level. Raw video frame files—originally recorded for every 1/30th second—will be aggregated into bins for analysis to reflect the duration of facial behaviors as the interaction progresses (Fairbairn et al., 2013; Sayette et al., 2012). Effects of time within the drink period will be entered at level-1 and treated as random at levels 2 and 3. Models for self-reported mood data will involve 2 levels –between-person and dyad-level. Alcohol condition and social familiarity will be entered at the dyad-level as predictor variables. Self-reported positive and negative mood as well as perceived social reinforcement will be each entered at the individual-level as the dependent variables.

Analysis of ambulatory data will also involve HLM, accounting for clustering of observations (level-1) within individuals (level-2). Note that, although ambulatory data will include some complete friendship dyads, we do not anticipate significant clustering at the level of these dyads, although ICC's will be calculated to confirm. An index of BAC and familiarity will be available for each observation, and these variables will be entered at level-1. Follow-up analyses will then parse within-person from between person effects—predictors will be centered according to the individual mean at level-1, and then individual averages will be entered at level-2. Level-1 covariates will include time of day, day of the week, limb of the BAC curve, and physical drinking context and level-2 covariates will include basic demographic variables (gender, age, and personality) (Miranda et al., 2014; Piasecki et al., 2011).

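### The ambulatory models have no recruitment-source term although the sample may combine laboratory completers with community recruits, so person-average BAC and familiarity effects are open to confounding by source

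*Combined protocol and SAP*

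**What the plan says.** The Study Protocol, at the end of its description of the laboratory session, allows two routes into the ambulatory part: "This opportunity may be offered to a subset of individuals who complete the laboratory study, as well as individuals recruited from the local community". It does not say how the subset is picked or how many people come by each route.

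The second paragraph of the Statistical Analysis Plan gives the ambulatory model. It has two levels, "accounting for clustering of observations (level-1) within individuals (level-2"), with BAC and familiarity entered at level 1. Within-person and between-person effects are separated only in follow-up analyses, where "predictors will be centered according to the individual mean at level-1, and then individual averages will be entered at level-2". The observation-level adjustment reads "Level-1 covariates will include time of day, day of the week, limb of the BAC curve, and physical drinking context". The person-level adjustment reads "level-2 covariates will include basic demographic variables (gender, age, and personality"). The plan has no recruitment-source term, no interaction with source, no stratified analysis and no analysis restricted to laboratory completers.

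**The concern.** The two routes need not deliver similar people. Laboratory completers entered through friendship groups, went through a filmed session with an assigned beverage and assigned company, and finished it. Nothing says that community recruits did any of this. Average drinking, usual company and average mood could all differ between the two groups, and gender, age and personality need not capture the difference.

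The estimates are exposed to different degrees:

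- The person-average effects compare people with one another, so a source difference in both average BAC (or familiarity) and average mood enters them directly.
- The uncentred level-1 effects fitted first blend within-person and between-person information, so they carry some of the same bias.
- The centred within-person effects are safe from mean differences. If the effect of BAC or familiarity itself differs by source, however, they estimate an average whose weights depend on a mix that the plan does not state.

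At stake is whether a between-person association in daily life reflects drinking or company, or only the route by which people were recruited.

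**Working it through.** **1. Figures in the plan.** The documents give no sample size, source share, effect size or variance for the ambulatory part, so there is no planned figure to reproduce. Every number below rests on stated assumptions.

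**2. Bias in the person-average slope.** Let s be the share of community recruits. Let dB be the source difference in average BAC, in within-source SDs. Let dM be the source difference in average mood, in SDs, that is not caused by BAC. Both are differences left after the planned covariates. If source is omitted, then:

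- covariance of average BAC with source = s(1−s) × dB
- variance of average BAC = 1 + s(1−s) × dB²
- bias = s(1−s) × dB × dM / (1 + s(1−s) × dB²)

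With s = 0.5, s(1−s) = 0.25:

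| dB | dM | Calculation | Bias (SD of mood per within-source SD of BAC) |
|---|---|---|---|
| 0.5 | 0.3 | 0.0375 / 1.0625 | 0.035 |
| 1.0 | 0.5 | 0.125 / 1.25 | 0.10 |

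The bias is zero if either difference is zero, and its sign is that of dB × dM. The same formula applies to average familiarity.

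**3. Level-1 slopes.** A person-mean-centred predictor averages zero within each person, so it is uncorrelated with any person-level variable, including source. A small simulation illustrates this. It used a random-intercept model with 100 people, 40 observations each and 6 runs per row. Community recruits were shifted by 0.5 in BAC (between-person SD 0.5, so 1 SD) and by 0.5 in mood (between-person SD 1, so 0.5 SD). These are the larger differences in step 2.

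| Community share | True slopes (lab, community) | Uncentred | Centred | Centred + source main effect | Interaction model: lab | Interaction model: community |
|---|---|---|---|---|---|---|
| 25% | 0.3, 0.3 | 0.299 | 0.298 | 0.298 | 0.300 | 0.292 |
| 50% | 0.3, 0.3 | 0.315 | 0.313 | 0.313 | 0.323 | 0.303 |
| 75% | 0.3, 0.3 | 0.315 | 0.314 | 0.314 | 0.311 | 0.315 |
| 25% | 0.3, 0.1 | 0.253 | 0.252 | 0.252 | 0.306 | 0.085 |
| 50% | 0.3, 0.1 | 0.197 | 0.197 | 0.197 | 0.290 | 0.104 |
| 75% | 0.3, 0.1 | 0.157 | 0.157 | 0.157 | 0.307 | 0.107 |

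- Equal slopes: the centred estimate stays near 0.30. With 6 runs, departures of about 0.015 are consistent with simulation noise.
- Equal slopes, uncentred: this estimate exceeds the centred one by only 0.001 to 0.002, because with 40 observations per person the within-person information dominates. The leakage would grow with fewer observations or less within-person variation in BAC.
- Unequal slopes: the pooled slope tracks the mix. For example, 0.5 × 0.3 + 0.5 × 0.1 = 0.20, against 0.197 simulated. A source main effect leaves it unchanged; the interaction approximately recovers both slopes.

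**The case against.** The strongest case against is that the harm depends on source differences for which the documents give no evidence. The planned covariates may absorb part of any such difference, person-mean centring already protects the within-person effects, and person-average associations are observational whatever is done. All of this stands as a limit on size. It does not remove the gap, because centring comes only in the follow-up analyses and does nothing for the person-average terms that those analyses add.

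Four stronger readings are tempting but are not supported:

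- *That the laboratory and daily-life results cannot be compared because the people differ.* The title speaks of "A Multimodal Investigation Integrating Laboratory and Ambulatory Methods", but the Statistical Analysis Plan specifies no test between the two parts. One part is a randomised beverage contrast and the other a slope on estimated BAC. They differ in much besides sample, so a source term would not make agreement or disagreement attributable to setting.
- *That the ambulatory part abandons a study-wide safeguard.* The Study Protocol describes a procedure "in which all participants are recruited through a single mechanism", but its stated purpose is "to ensure that the populations of individuals in friend and stranger conditions are comparable and unaffected by selection bias". That protects a contrast within the laboratory and was never promised for the ambulatory part.
- *That community recruits are unscreened.* The eligibility paragraph precedes the laboratory description and is worded for participants in general, so it may already cover them. Shared criteria would narrow the differences, but would leave friendship-group entry, session exposure and completion as possible ones.
- *That laboratory participants are hand-picked, or that a known fraction had alcohol or a stranger.* The text states neither a selection rule nor an allocation ratio.

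**Conclusion.** The point holds as a gap in the adjustment of the ambulatory models. Two sources are permitted and nothing in the model distinguishes them. The person-average BAC and familiarity effects are directly exposed. The uncentred level-1 effects are exposed in principle, though probably only slightly where each person contributes many observations. The centred effects are exposed only if the effects themselves differ by source.

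The size cannot be derived from the documents. The range of about 0.035 to 0.10 SD in the person-average slope assumes a 50:50 mix and residual differences of 0.5 to 1 SD in BAC and 0.3 to 0.5 SD in mood. Smaller differences or a more lopsided mix would shrink it. The randomised laboratory comparison is not affected. The change is worth making because it is cheap, not because serious bias has been shown.

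**What to change.** In the ambulatory section of the Statistical Analysis Plan:

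1. Add recruitment source (laboratory completer or community) as a level-2 covariate in every ambulatory model. This addresses the confounding of the person-average and uncentred effects.
2. As a secondary check, add source-by-BAC and source-by-familiarity interactions. The main effect alone does nothing for effects that differ by source.
3. Report a sensitivity analysis in laboratory completers only, and use it wherever ambulatory results are discussed alongside the laboratory results.

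Source should be recoverable from enrolment records, since completers have a laboratory session on file. No new participants or procedures are needed. The cost is one extra covariate and a completer-only estimate that is less precise than the pooled one. With no sample size stated, the precision of that estimate and of the interactions cannot be given in advance, so a non-significant interaction should not be read as showing equal effects.

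### Familiarity appears to be set for a four-person session, but the laboratory models stop at the dyad, so its standard error is too small if both dyads of a session are analysed and friends or session-mates are alike

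*Combined protocol and SAP*

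**What the plan says.** **Design (Study Protocol, laboratory portion).** "Two friend dyads are invited to the laboratory for simultaneous beverage administration sessions". On the day, "they are randomly assigned to consume alcohol in the company of their own friend, or of the friend of the other participant". Beverage is described as a separate draw: "Dyads will be randomly assigned to receive either a moderate dose of alcohol or a control beverage". For the stranger condition the protocol adds that "backup participants are invited to all stranger sessions in case the primary 2 participants are previously acquainted".

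**Analysis (Statistical Analysis Plan, first paragraph).** The facial model has three levels, of which the dyad is the highest. For self-reports, "Models for self-reported mood data will involve 2 levels", again ending at the dyad. "Alcohol condition and social familiarity will be entered at the dyad-level as predictor variables". There is no session term, no friend-pair term and no session-robust standard error.

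**Contrast (Statistical Analysis Plan, second paragraph).** For the ambulatory data the plan does consider friend-pair clustering: "we do not anticipate significant clustering at the level of these dyads, although ICC's will be calculated to confirm". No such check is planned for the laboratory data.

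**The concern.** Four people from two friend pairs can be paired in three ways. One gives two friend dyads, two give two stranger dyads, and none gives one of each. The protocol implies, without stating it, that both dyads of a session share one familiarity condition, and it speaks of stranger sessions as a unit. A factor set for a cluster should be tested against variation between clusters. Testing it against variation between dyads gives too small a standard error and too many degrees of freedom if the two dyads of a session are correlated.

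There are two routes to such correlation:

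- **Shared session.** Both dyads attend on the same occasion.
- **Split friend pairs.** In a stranger session each dyad holds one member of each friend pair, so similarity between friends correlates the two dyads even without a session effect. Friends are recruited as same-gender, and gender is listed as a covariate only for the ambulatory models. Any gender difference in mood or facial behaviour would therefore remain in the laboratory residual structure.

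At stake is the error rate of the main effect of familiarity, one of the two experimental factors.

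**Working it through.** **Inputs.** From the documents: two dyads of two people per session, familiarity common to the session, and dyad as the top model level. The documents give no ICC, sample size, alpha or power, so there is no figure of the plan's own to reproduce. Assumed: total variance 1, two-sided 5%, and 40 sessions (80 dyads, 20 sessions per familiarity arm). Variance shares are session vs, friend pair vf, dyad vd and individual ve = 1 − vs − vf − vd. vd is 0.2 when vs = 0 and 0.1 otherwise.

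**Variances of dyad means**

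- Friend session: Var = vs + vf + vd + ve/2. Covariance of the two dyads = vs.
- Stranger session: Var = vs + vf/2 + vd + ve/2. Covariance = vs + vf/2.

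With K sessions per arm, the true variance of an arm mean is (Var + Cov)/(2K). A dyad-level model reports Var/(2K). Summed over the two arms:

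naive/true variance = (Var_F + Var_S) / (Var_F + Var_S + Cov_F + Cov_S)

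Large-sample type I error = 2 × [1 − Φ(1.96 × √ratio)].

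**Worked cases**

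- vs = 0, vf = 0.1, vd = 0.2, ve = 0.7: (0.65 + 0.60)/(1.25 + 0 + 0.05) = 0.962. SE ratio 0.98, error 5.5%.
- vs = 0, vf = 0.2, vd = 0.2, ve = 0.6: (0.70 + 0.60)/(1.30 + 0 + 0.10) = 0.929. SE ratio 0.96, error 5.9%.
- vs = 0.1, vf = 0.3, vd = 0.1, ve = 0.5: (0.75 + 0.60)/(1.35 + 0.10 + 0.25) = 0.794. SE ratio 0.89, error 8.1%.

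**Simulation.** Dyad means were analysed with alcohol, familiarity and their product, with beverage drawn per dyad, in 20,000 replicates at 40 sessions:

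| Session share | Friend-pair share | Naive/true SE (formula) | Familiarity type I error (formula) | Familiarity type I error (simulated) |
|---|---|---|---|---|
| 0 | 0 | 1.00 | 5.0% | 5.1% |
| 0 | 0.1 | 0.98 | 5.5% | 5.3% |
| 0 | 0.2 | 0.96 | 5.9% | 5.9% |
| 0 | 0.3 | 0.95 | 6.3% | 6.4% |
| 0.05 | 0.2 | 0.93 | 6.9% | 6.6% |
| 0.1 | 0.1 | 0.91 | 7.4% | 7.6% |
| 0.1 | 0.2 | 0.90 | 7.7% | 7.8% |
| 0.1 | 0.3 | 0.89 | 8.1% | 7.7% |

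Over the non-zero shares the simulated range is 5.6% to 8.0% at 20 sessions and 5.3% to 7.9% at 80, so more sessions do not cure it.

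**Fixed dyad share.** With vd held at 0.1 throughout, the formula gives 5.5%, 6.0% and 6.4% for friend-pair shares of 0.1, 0.2 and 0.3 alone. It gives 6.0% and 7.0% for session shares of 0.05 and 0.1 alone, and 7.4% with both at 0.1.

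**Other tests.** With beverage drawn per dyad, alcohol is 4.8% to 5.3% and alcohol × familiarity 4.8% to 5.1%. They move away from 5% only if allocation is forced within the session. At vf = 0.3, vs = 0.1 they are 8.7% and 8.5% if the two dyads must share a beverage, and 2.3% and 2.4% if they must differ.

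**Remedies at 40 sessions (familiarity).** A session random effect (REML, 38 df) gives 4.1% to 5.2%, session-clustered CR2 standard errors (38 df) 4.8% to 5.5%, and a t-test on session means 4.7% to 5.3%.

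**The case against.** **Perhaps only one stranger dyad per session is analysed.** The wording about backups ("backup participants are invited to all stranger sessions in case the primary 2 participants are previously acquainted") refers to two people, not four, and fits a single target dyad. Backups may also disturb the clean swap. This stands as a condition: with one stranger dyad per session, the familiarity error is 4.2% to 5.2%. It is not a complete escape. If friend sessions still supply both dyads and only session variance exists (vs = vd = 0.1, ve = 0.8), the ratio is (0.6/40 + 0.6/20)/(0.7/40 + 0.6/20) = 0.045/0.0475 = 0.947, an error of about 5.6%. That is marginal.

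**The ICCs are unknown, and the larger figures need a generous session effect.** A session share of 0.1 equals the assumed dyad share, although the protocol suggests that dyads drink apart. This is fair. Friend similarity alone gives only 5.3% to 6.4%. The authors' expectation of little friend-pair clustering concerns the ambulatory data and is itself to be checked there.

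**The affected test is narrow.** The title points to alcohol's effect and how context changes it, not to friend versus stranger. The alcohol and interaction tests do stay close to nominal if beverage is drawn per dyad, and the forced-allocation figures describe schemes that the protocol does not state. But no primary test is named, and familiarity is one of the two laboratory predictors.

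**The facial model was not simulated in full.** Correct. The calculation uses dyad means, so it bears on mood and on average facial level. It gives no magnitude for familiarity-by-time effects.

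**Conclusion.** The concern holds, conditionally. The design makes familiarity in effect a session-level factor, and the laboratory models have no level above the dyad. If both dyads of a session are analysed, and there is any session or friend-pair similarity, the familiarity main effect is tested with a standard error that is too small: 2% to 11% under the assumed shares, for an actual error of 5.3% to 7.8% at nominal 5%. The effect is modest if only friends are alike and larger with session effects. The alcohol and interaction tests are not affected under independent dyad-level beverage draws. All magnitudes rest on assumed variance shares and 40 sessions. This should be fixed but is not fatal, and confidence is moderate because the SAP does not say which dyads are analysed.

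**What to change.** In the SAP's laboratory paragraph:

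1. Add session as the top random level in the mood and facial models, or use session-clustered standard errors with a small-sample correction. Test familiarity with session-based degrees of freedom.
2. State whether both stranger dyads of a session are analysed, how backups are handled, and how beverage is drawn within a session.
3. Report session and friend-pair ICCs for the laboratory outcomes, as already planned for friendship dyads in the ambulatory data.

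A friend-pair effect crossed with dyad is optional and not needed for a valid familiarity test. Friend pair and dyad coincide in friend sessions, so it would have to assume equal variances across arms.

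**Cost.** Two or three sentences, and a record of who attended together and who came with whom. The documents do not say whether those identifiers are in the analysis file. The familiarity standard error becomes about 2% to 12% larger under the assumed shares (1/0.98 to 1/0.89). At 40 sessions the degrees of freedom fall from 80 − 4 = 76 to 40 − 2 = 38, and the critical value rises from 1.99 to 2.02 (+1.6%). If there is no clustering, the session random effect is slightly conservative (4.1%).

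### Does the ambulatory model need its random slopes and standard errors written into the plan to protect the BAC and familiarity tests?

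*Combined protocol and SAP*

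**What the plan says.** The second paragraph of the Statistical Analysis Plan sets out a two-level model for the ambulatory data, "accounting for clustering of observations (level-1) within individuals (level-2". On the predictors it says: "An index of BAC and familiarity will be available for each observation, and these variables will be entered at level-1". A follow-up model separates within-person from between-person effects: "predictors will be centered according to the individual mean at level-1, and then individual averages will be entered at level-2". Adjustment is by fixed covariates: "Level-1 covariates will include time of day, day of the week, limb of the BAC curve, and physical drinking context". The only further dependence it mentions is between friends, for which intraclass correlations will be calculated.

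The first paragraph is more explicit about the facial data: "Effects of time within the drink period will be entered at level-1 and treated as random at levels 2 and 3". The ambulatory paragraph has no matching sentence. It names no day level, residual correlation structure or standard-error method, and it rules none of them out.

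The Study Protocol gives the data volume: monitors "assess alcohol use during the ambulatory assessment period, lasting 14 days", with survey "alarms sounding 8 times during their waking hours". It introduces this component with: "Participants may also be offered the opportunity to participate in an additional ambulatory study".

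**The concern.** Each person supplies many prompts, and the tests of interest are on level-1 predictors. A random intercept absorbs differences in average mood. It does not absorb differences between people in how strongly mood responds to BAC or familiarity, nor a person's own good and bad days. The covariates do not fill that gap, because time of day and day of the week remove only patterns common to everyone. Person-mean centring changes which effect is estimated, not its error structure.

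So an intercept-only fit with model-based standard errors, which the text permits, could overstate the evidence for the average effects of BAC and familiarity. Recruiting more people would not cure it. The explicit random effects in the facial model make the silence here more noticeable, and an unwritten choice could in principle be made after seeing the data.

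**Working it through.** The plan has no sample size, power or alpha for this component, so there is no stated figure to reproduce. The check is how far a nominal 5% two-sided test could drift **if** the model were intercept-only with model-based standard errors.

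**From the documents.** 14 days and 8 prompts. Read as 8 per day (an assumption), that is 14 × 8 = 112 prompts per person.

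**Assumed.** 70% of prompts answered (0.7 × 112 ≈ 78); total mood variance 1 with person ICC 0.4, so residual variance 0.6; familiarity with 20% between-person variance, so within-person variance 0.8; overall SD of BAC 0.0197%. Slope SDs are in mood SD, per SD of familiarity or per 0.08% BAC.

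**Formulas.** Actual error = 2 × [1 − Φ(1.96/√DE)], where DE is the true variance of the estimate divided by the variance the intercept-only model assumes.

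- Slope variation: DE = (1 + m·r)/(1 + r), with m prompts and r = slope variance × within-person predictor variance / residual variance.
- Day effect, 8 prompts a day: DE = 1 + 7 × (predictor day ICC) × (residual day ICC).
- Serial correlation: DE = (1 + ρxρe)/(1 − ρxρe), for predictor and residual lag-1 correlations ρx and ρe.

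**Slope variation, m = 78.** For familiarity with slope SD 0.1, r = 0.01 × 0.8/0.6 = 0.0133, DE = 2.04/1.0133 = 2.01, and error is 16.7%. For BAC with slope SD 0.2, the slope SD per SD of BAC is 0.2 × 0.0197/0.08 = 0.049, r = 0.049²/0.6 ≈ 0.0040, DE ≈ 1.31, and error is 8.7% if all BAC variance is within-person (8.3% if 90% is). Halving the slope SDs gives 8.0% and 5.9%.

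**Day and serial correlation.** Predictor day ICC 0.5 with residual day ICC 0.1 gives DE = 1.35 and 9.2%; 0.2 with 0.05 gives 1.07 and 5.8%. Lag-1 correlations of 0.3 and 0.2 give DE = 1.06/0.94 = 1.13 and 6.5%. Set either member of a pair to zero and DE = 1, so error is 5.0%. Correlated mood alone is not enough; the predictor must be correlated too.

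**Simulation of the full covariate model.** 60 people, about 78 prompts each, 4,000 replicates per row, true effects zero. BAC runs over consecutive evening prompts and familiarity has lag-1 within-day correlation 0.5. The test uses a random intercept and model-based standard errors.

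| Assumed extra structure | BAC | Familiarity |
|---|---|---|
| None | 5.0% | 4.9% |
| Day variance 5%, serial 0.15 | 6.5% | 7.3% |
| Day variance 10%, serial 0.3 | 8.8% | 8.3% |
| Slope SDs 0.1 / 0.05 | 5.7% | 7.6% |
| Slope SDs 0.2 / 0.1 | 8.4% | 16.5% |
| Smaller day/serial and smaller slopes | 7.3% | 9.9% |
| Larger day/serial and larger slopes | 11.6% | 20.2% |

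The slope rows agree with the closed form. The last row hardly moves with 30 people (12.1% / 20.3%) or 120 (11.8% / 20.1%). The person-mean-centred model gives the same last row.

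**How wide the unknown is.** At 112 prompts the slope formula alone runs from 5.0% (r = 0) through 8.3% (r = 0.0025) and 17.6% (r = 0.01) to 43.4% (r = 0.05). Nothing in the documents places this study on that scale.

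**What an ordinary alternative does.** With the same 60-person inputs and the 30- and 120-person variants, person-clustered jackknife standard errors held 4.4-5.8%, and random slopes for BAC and familiarity held 3.7-5.3%. Either usual choice is enough under these inputs, without a day level or serial term.

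**The case for a change.** The best case for a change is that the omission is real, the facial model shows the authors can state random effects, many prompts per person magnify small differences in slope, and two sentences would close off a choice made after seeing results. Cluster-robust standard errors also cost almost nothing when there is no extra variation (mean jackknife standard error 1.00 / 1.01 of the true one). The mechanism and the arithmetic stand.

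It does not follow that the plan is wrong. The harmful model has to be supplied by the reader, since the text neither states nor implies that slopes are fixed or standard errors model-based. The facial-model sentence cuts both ways: it does not reach BAC or familiarity, but it shows that random level-1 effects are within the intended framework. The part due to slope variation also matters only for inference about the average effect across people.

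Nor is the obvious insertion clearly right. Clustering on the person ignores the complete friendship dyads that the plan expects in these data. As an assumed illustration, a correlation of 0.2 between partners' person-level estimates with everyone in a dyad gives DE = 1.2 and about 7.4% error; with half the people in dyads, DE = 1.1 and about 6.2%. That matches the smaller inflations in the table. The level of clustering is better settled after the dyad ICC check that is already planned.

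**Conclusion.** The concern does not call for a change. The plan is silent on random slopes and standard errors for the ambulatory model, and an analyst who took the barest reading could run tests at about 6-12% (BAC) and 7-20% (familiarity) in place of 5%. Those figures assume a 5% two-sided level, 8 prompts per day, 70% compliance, and slope, day and serial variances that appear nowhere in the documents. They return to 5% if slopes do not vary and mood and predictor are not both correlated within days. The named method includes the usual remedies, and an experienced multilevel analyst would choose among them with the data structure and the dyad ICCs in view. This is a gap in detail, not a stated rule that gives a wrong answer, and it is confined to the additional ambulatory study. The randomised beverage and familiarity comparisons in the laboratory are unaffected. A reader of the eventual results need only check which random effects and standard errors were reported.
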